### 2.1.4.3 Deaths

The deaths observation period are per the observation periods defined above.

- Death on-study: deaths occurring during the on-study observation period.
- Death on-treatment: deaths occurring during the TEAE period.
- Death post-study: deaths occurring after the end of the study.

#### 2.1.4.4 Laboratory safety variables

Clinical laboratory data consists of blood analysis (including hematology, clinical chemistry, amylase, lipase and lipid profile) and urinalysis. Clinical laboratory values will be summarized in both standard international units and conventional units when applicable.

Blood samples for clinical laboratories will be collected at designated visits (see study flowchart in [D](#)). The following laboratory data will be measured at a central laboratory:

- Hematology
  - Red blood cells and platelets: hemoglobin, hematocrit, red blood cell, platelets count,
  - White blood cells: white blood cell, neutrophils, lymphocytes, monocytes, basophils, eosinophils.
- Clinical chemistry
  - Metabolism: glucose (serum), creatine phosphokinase (CPK),
  - Electrolytes and minerals: sodium, potassium, chloride, bicarbonate (ie, carbon dioxide), calcium, phosphorus, magnesium,
  - Renal function: blood urea nitrogen (BUN), creatinine, uric acid,
  - Liver function: total protein, albumin, ALT, aspartate aminotransferase (AST), alkaline phosphatase (ALP), total bilirubin, Lactic acid dehydrogenase (LDH).
- Lipid parameters (fasting): total cholesterol (TC), high density lipoprotein cholesterol (HDL-C), low density lipoprotein cholesterol (LDL-C) (calculated by Friedwald equation, See [Section 2.5.1](#)), Non-HDL-C (calculated as the difference between TC and HDL-C), triglycerides (TG).
- Pancreatic enzymes: lipase, amylase.

Urine samples will be collected at designated visits (see study flowchart in [D](#)). The following laboratory data will be measured at a central laboratory:

- Urine dipstick includes: specific gravity, pH, protein, blood, ketones, bilirubin, urobilinogen, nitrite, and leukocyte esterase.
- Urine microscopy includes, but is not limited to: detection of formed cellular elements, casts, bacteria, yeast, parasites, and crystals in centrifuged urine sediment.

Serum glucose will be presented as efficacy parameters in [Section 2.4.4](#). For creatinine and calculated eGFR, Potentially Clinically Significant Abnormality (PCSA) summaries will be presented in the safety section while descriptive summaries in the efficacy section.

Technical formulas are described in [Section 2.5.1](#).

#### **2.1.4.5 Vital signs variables**

Vital signs include: heart rate (HR), systolic and diastolic blood pressure, temperature, and respiratory rate. They will be performed after the patient has been seated for at least 5 minutes. Blood pressure and HR will be assessed 3 times with at least 1 minute between each measurement. The mean of the 3 measurements will be analyzed for each vital sign variable (HR, SBP, and DBP).

#### **2.1.4.6 Physical examination**

A complete physical exam will be performed at Visit 1 (Screening), Visit 9 (Week 26) and Visit 13 (Week 79). “Normal”, “Abnormal” or “Not done” as determined by the Investigator will be reported in the e-CRF by body system.

#### **2.1.4.7 Electrocardiogram variables**

12-lead ECGs will be performed at Visit 1 (Screening), Visit 9 (Week 26), and Visit 13(Week 79). ECG status of “normal” or “abnormal” will be reported in the e-CRF as determined by the investigator.

#### **2.1.5 Pharmacokinetic variables**

Pharmacokinetic variables include the plasma concentration of sotagliflozin and its 3-O-glucuronide metabolite in the sotagliflozin 400 mg group.

## **2.2 DISPOSITION OF PATIENTS**

This section describes patient disposition for both patient study status and the patient analysis populations.

Screened patients are defined as all patients who have signed the informed consent.

Randomized patients consist of all patients with a signed informed consent form who have had a treatment kit number allocated and recorded in the IRT database, regardless of whether the treatment kit was used or not.

For patient study status, the total number of patients in each of the following categories will be presented in the CSR using a flowchart diagram or summary tables:

- Screened patients.
- Run in patients: patients who had a run-in record in IRT.
- Screen failure patients (including failures during run-in) and reasons for screen failure.
- Nonrandomized but treated patients.
- Randomized patients.

- Randomized but not treated patients.
- Randomized and treated patients.
- Patients who have completed the 26-week double-blind core treatment period (see [Section 2.5.4](#)) as per protocol.
- Patients did not complete the 26-week double-blind core treatment period (see [Section 2.5.4](#)) as per protocol and the reasons for permanent treatment discontinuation.
- Patients who have completed the 79-week entire treatment period as per protocol (double-blind core treatment period and extension treatment period).
- Patients who did not complete the 79-week entire treatment period as per protocol, and the reasons for permanent treatment discontinuation.
- Patients who have completed the study as per protocol.
- Patients who did not complete the study as per protocol and the reasons for study discontinuation.
- Patients' end of study status (completed, not completed) and corresponding end of entire treatment status (completed, not completed).
- Status at last study contact.

For screened, run in, screen failure, and nonrandomized but treated patients, percentages will be calculated using the number of screened patients as the denominator. All other categories of patients will be presented by treatment group and the percentages will be calculated using the number of randomized patients within each treatment group as the denominator. Reasons for treatment discontinuation will be supplied in tables giving numbers and percentages by treatment group. Patients prematurely discontinued from treatment and/or study, along with reasons for discontinuation, will also be listed.

A summary of the distribution of patients by country and center will also be provided (overall number of patients screened, run-in, randomized, and treated, as well as number of patients randomized, discontinued from study treatment, and discontinued from study for each treatment group).

Patients treated but not randomized, patients randomized but not treated and patients randomized but not treated as randomized will be identified and described in separate listings. The patients of the third category (randomized and not treated as randomized) will be part of efficacy and safety analyses ([Section 2.3](#)). Patients randomized but not treated will be included in efficacy analysis. Safety data of patients treated but not randomized will be reported separately.

The randomization strata [HbA1c at Screening ( $\leq 8.5\%$ ,  $> 8.5\%$ ), Metformin use at screening (Yes, No), and mean SBP at Screening ( $< 130$ ,  $\geq 130$  mmHg)] assigned by IRT will be summarized. The percentages will be calculated using the number of randomized patients as the denominator. The discrepancy between the strata assigned by IRT and the information reported on e-CRF will be listed for all randomized patients.

Kaplan-Meier (KM) plots of the cumulative incidence of double-blind IMP discontinuations due to any reason and due to AE will be provided for the entire 79-week double-blind treatment period separately. A listing of these patients, along with the reason for discontinuation of treatment, study completion status and the reason for discontinuation study, will be provided.

All important deviations including randomization and drug-dispensing irregularities will be summarized in tables giving numbers and percentages of deviations by randomized treatment group.

Additionally, the analysis populations for safety, efficacy, and pharmacokinetics defined in [Section 2.3](#) will be summarized in a table by number of patients in the randomized population.

- Efficacy population: intent-to-treat (ITT) population.
- Safety population.
- PK population.

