10.3.3 List of criteria for permanent treatment discontinuation

Patients may withdraw from treatment with the IMP at any time for any reason or this may be the Investigator's decision. Patients should discuss stopping study medication with the site before doing so in order that questions can be addressed, glycemic therapy adjusted, and a follow-up assessment arranged. All efforts should be made to document the reasons for treatment discontinuation and this should be documented in the e-CRF.

The following reasons lead to permanent discontinuation:

- At the patient's own request (ie, withdrawal of consent for treatment)
- If, in the Investigator's opinion, continuation with the administration of the study treatment would be detrimental to the patient's well-being
- Inter-current condition that requires permanent discontinuation of the study treatment as long as the abnormality persists and if the casual relationship of the concerned event and the IMP is possible (according to the Investigator's best medical judgment)
- Pregnancy (in female patients)
- Specific request of the Sponsor

[figure not shown]
Any abnormal laboratory value will be immediately rechecked to confirm the result before a decision is made to permanently discontinue IMP for the concerned patient.

For patients who prematurely discontinue the IMP, the assessments planned at the EOT visit (see [Section 10.1.3.2](#)) will be performed at the Premature EOT Visit, scheduled preferably prior to treatment discontinuation or as soon as possible after the time of discontinuation (the latest at the next scheduled on-site visit). The reason(s) for IMP discontinuation will be clearly specified. This Premature EOT assessment may occur at a regularly scheduled visit or at an unscheduled visit.

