### 1.3 DETERMINATION OF SAMPLE SIZE

The sample size/power calculations are based on the primary variable, change from Baseline to Week 26 in HbA1c. Assuming a common standard deviation (SD) of 1.2% and using a 2-sided test at a 0.05  $\alpha$ -level, 250 patients per arm will have 99% power to detect a treatment difference of 0.6% in mean HbA1c change from Baseline to Week 26 between sotagliflozin 400 mg and placebo.

The number of patients taking a sulfonylurea and metformin will be limited to 330 patients, to ensure sufficient numbers of sulfonylurea monotherapy patients.

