### ***Time to event analysis***

For time to event analysis/KM plot, time to event (eg, treatment discontinuation, rescue therapy, hypoglycemia, etc) is defined as the number of days from the date of the first administration of double-blind IMP (or the date of randomization if not exposed) to the start date of the first occurrence of the event during the 79-week double-blind treatment period.

Patients who did not experience any event during the 79-week double-blind treatment period are considered censored observations. For time to treatment discontinuation/rescue therapy, censoring date is the date of EOT. For time to severe or documented hypoglycemia, censoring date is date of EOT+1 or date of EOS, whichever is the earliest. Date of EOS will be used if date of EOT is not available. Last contact date will be used if date of EOS is not available.

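### The curve for IMP discontinuation due to AE is labelled cumulative incidence but is a Kaplan-Meier estimate that censors stops for other reasons; the two differ, by a small amount, once AE stops follow other stops

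*SAP*

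**What the plan says.** SAP 2.2 plans the following for the 79-week double-blind period: "Kaplan-Meier (KM) plots of the cumulative incidence of double-blind IMP discontinuations due to any reason and due to AE will be provided". There are two curves, one for any reason and one for AE, both estimated by Kaplan-Meier and both described as cumulative incidence.

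The computing rule is in SAP 2.5.4 under Time to event analysis. It covers this endpoint by name: "time to event (eg, treatment discontinuation, rescue therapy, hypoglycemia, etc) is defined as the number of days from the date of the first administration". It then says "Patients who did not experience any event during the 79-week double-blind treatment period are considered censored observations", and "For time to treatment discontinuation/rescue therapy, censoring date is the date of EOT". It makes no exception for a patient whose treatment ended for a reason other than the one being plotted. Neither document mentions competing risks, and SAP 2.5.7 (Statistical technical issues) lists none.

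SAP 2.2 also reports the crude figures: "Reasons for treatment discontinuation will be supplied in tables giving numbers and percentages by treatment group", where "the percentages will be calculated using the number of randomized patients within each treatment group as the denominator".

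**The concern.** Protocol 10.3.2 defines permanent discontinuation as a definitive decision not to expose the patient to IMP again. After such a stop for a non-AE reason, discontinuation due to AE can no longer occur. The patient's outcome is known and excludes the event; it is not merely unobserved. Kaplan-Meier with censoring instead treats the patient as still open to the same AE-stop hazard as those who remain on treatment. One minus Kaplan-Meier then describes a hypothetical setting without other stops, which is not the quantity the SAP names.

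Non-AE stops are foreseen. Protocol 10.3.3 lists, among others, "At the patient's own request (ie, withdrawal of consent for treatment" and a specific request of the sponsor, and Protocol 8.7.1 allows discontinuation for continued poor compliance.

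What is at stake is agreement within the study report. The end of the AE curve and the AE row of the disposition table would be read as the same quantity and could show different values. The any-reason curve is not affected, because every discontinuation counts as an event there.

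**Working it through.** **Inputs.** The estimator, label and censoring rule come from SAP 2.2 and 2.5.4. The arm size of 250 comes from SAP 1.3 ("250 patients per arm will have 99% power to detect a treatment difference of 0.6% in mean HbA1c change"). The documents give no expected discontinuation rate by reason and no figure for this curve, so there is nothing to reproduce. All rates below are assumptions, shown over a range.

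**Formulas, constant cause-specific hazards.** Let A and O be the true (crude) Week 79 risks of stopping for AE and for other reasons.
- Total cumulative hazard: H = −ln(1 − A − O)
- AE part: H_A = H × A/(A + O); other part: H_O = H − H_A
- Kaplan-Meier reading: 1 − exp(−H_A)
- Cumulative incidence: H_A/(H_A + H_O) × (1 − exp(−(H_A + H_O))), which returns A

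**Example.** With A = 5% and O = 15%, H = −ln(0.80) = 0.2231, H_A = 0.2231 × 0.05/0.20 = 0.0558, and the Kaplan-Meier reading is 1 − exp(−0.0558) = 5.43%.

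**Range.**

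| Other stops | Reading, true AE risk 5% | Excess (points) | Ratio | Reading, true AE risk 2% |
|---|---|---|---|---|
| 5% | 5.13% | 0.13 | 1.03 | 2.05% |
| 10% | 5.27% | 0.27 | 1.05 | 2.11% |
| 15% | 5.43% | 0.43 | 1.09 | 2.17% |
| 20% | 5.59% | 0.59 | 1.12 | 2.23% |
| 30% | 5.97% | 0.97 | 1.19 | 2.38% |

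A cumulative incidence function would end at 5.00% or 2.00% in every row. Outside this range the excess can pass one point: 8% AE with 30% other stops reads 9.57%.

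**Dependence on timing.** Take 250 patients with 12 AE stops (12/250 = 4.80%) and 25 other stops.
- All other stops first: the AE stops fall in a risk set of 250 − 25 = 225, so one minus Kaplan-Meier is 12/225 = 5.33%.
- Randomly mixed order: 5.06% on average over 4,000 simulated orderings.
- All other stops last: 12/250 = 4.80%, no excess.

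**Equal AE hazard in both arms.** Set H_A = −ln(0.95) = 0.0513, so Kaplan-Meier ends at 5.00% whatever the other stops do. Let H_O = −ln(1 − p), with p = 5%, 10%, 15%, 20% and 30%. The cumulative incidence is then 4.88%, 4.75%, 4.62%, 4.49% and 4.21%.

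**The case against.** The strongest defence is that Kaplan-Meier with other stops censored is a legitimate summary of the AE-specific hazard under independent censoring. For comparing tolerability between arms it has an advantage: at equal AE hazards the curves coincide, as the last step shows. The cumulative incidence function does not share this property. With an AE hazard of 0.0674 in both arms and other-stop hazards of 0.168 and 0.299 (assumed), Kaplan-Meier ends at 6.5% in both, while the cumulative incidence ends at 6.0% and 5.6%. The arm with more other stops looks better tolerated. This stands: the choice between the two is partly a choice of target, and changing the estimator has a price. But the SAP has named its target, and Kaplan-Meier does not estimate it.

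It also stands that the crude risk is available elsewhere. SAP 2.2 gives the count and percentage by reason and a listing of patients, and SAP 2.4.5.2 tabulates treatment-emergent AEs leading to discontinuation. The problem is confined to the curve and its label.

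Three stronger readings are tempting, and the documents do not support them.
- *The curves would show a false gap between arms when only the other reasons differ.* Suppose crude AE risk is 6% in both arms, with other stops of 15% and 25%. The curves end at 6.5% and 6.9%, but these inputs imply AE hazards of 0.0674 and 0.0718, so the gap reflects a hazard difference. It is also small: 0.4 points is one patient in 250, against a standard error of √(2 × 0.06 × 0.94/250) = 2.1 points for a difference between two 6% proportions.
- *The overstatement is always larger in the arm with more other stops.* This holds only with AE risk and timing equal. An arm with 6% AE and 8% other stops is overstated by 0.26 points; one with 2% AE and 15% other stops by 0.17.
- *Lack of efficacy on placebo will drive a marked imbalance.* It is not among the reasons in the available text of Protocol 10.3.3, and under Protocol 8.2.2 rescued patients continue blinded treatment. Such stops remain possible at the investigator's discretion, but the documents give no basis for expecting many.

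**Conclusion.** The point holds as a minor one about estimator and label. As specified, the AE curve is not a cumulative incidence. It lies above the cumulative incidence whenever some AE stops come after other-reason stops, and equals it if all other stops come later. Under constant hazards the excess is below one percentage point for an AE-stop risk up to 5% and other stops up to 30%, with a relative overstatement of 1.03 to 1.19 as other stops rise from 5% to 30%. These rates are assumptions, and the actual size depends on the rates and timing observed. The plot is descriptive: no test, efficacy conclusion or multiplicity step rests on it.

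**What to change.** In SAP 2.2, plot discontinuation due to AE as an Aalen-Johansen cumulative incidence function with other-reason permanent discontinuation as the competing event, and keep Kaplan-Meier for any-reason discontinuation. In SAP 2.5.4, add one line saying that for the AE-specific curve other-reason stops are competing events and are not censored at EOT.

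Because the cumulative incidence function also depends on the rate of other stops, show the any-reason curve, or the other-reason function, beside it so that a lower AE curve is not misread as better tolerability.

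If the sponsor prefers Kaplan-Meier for the AE curve, remove the cumulative incidence label and state that other-reason stops are censored.

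The cost is one phrase, one added line and a programming option. No new data are needed.

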### 2.2.1 Randomization and drug dispensing irregularities

Randomization and drug-dispensing irregularities occur whenever:

1. A randomization is not in accordance with the protocol-defined randomization method, such as a) an ineligible patient is randomized, b) a patient is randomized based on an incorrect stratum, c) a patient is randomized twice, or d) in a dynamic randomization scheme the treatment assignment is, in fact, not random, due to a computer program error.

OR

3. A patient is dispensed an IMP kit not allocated by the protocol-defined randomization, such as a) a patient at any time in the study is dispensed a different treatment kit than as randomized (which may or may not contain the correct-as-randomized IMP), or b) a nonrandomized patient is treated with IMP reserved for randomized patients.

Randomization and drug-dispensing irregularities will be monitored throughout the study and reviewed on an ongoing basis.

All randomization and drug-dispensing irregularities will be documented in the CSR. If the number of irregularities is large enough to make a tabular summary useful, the irregularities will be categorized and summarized among randomized patients (number and percentages). Nonrandomized, treated patients will be described separately. Listings with additional, relevant details will be provided in appendices.

Randomization and drug-dispensing irregularities to be prospectively identified include but are not limited to:

---

***Randomization and drug allocation irregularities***

---

*Kit dispensation without IRT transaction*

*Erroneous kit dispensation*

*Kit not available*

*Randomization by error*

*Patient randomized twice*

*Stratification error*

*Patient switched to another site*

---

## **2.3 ANALYSIS POPULATIONS**

Patients treated without being randomized will not be considered randomized and will not be included in any efficacy population.

The randomized population includes any patient who has been allocated to a randomized treatment regardless of whether the treatment kit was used.

For any patient randomized more than once, only the data associated with the first randomization will be used in any analysis population. The safety experience associated with any later randomization will be assessed separately.

The safety experience of patients treated and not randomized will be reported separately, and these patients will not be in the safety population.

### **2.3.1 Efficacy populations**

Efficacy analyses will be based on the treatment group allocated by the IRT according to the randomization schedule at randomization visit (as randomized), irrespective of the treatment actually received.

#### ***2.3.1.1 Intent-to-treat population***

Efficacy analyses will be based on the ITT population, defined as all randomized patients, irrespective of compliance with the study protocol and procedures. Patients will be analyzed for efficacy according to the treatment group to which they are randomized.

### **2.3.2 Safety population**

Safety analyses will be based on the safety population, defined as all randomized patients who receive at least one dose or part of a dose of double-blind IMP (regardless of the amount of treatment administered). Patients will be analyzed according to the treatment actually received.

In addition:

- Nonrandomized but treated patients will not be part of the safety population; however, their safety data will be presented separately.
- Randomized patients for whom it is unclear whether they took the IMP will be included in the safety population as randomized.
- When a patient is exposed to both placebo and sotagliflozin, the patient will be analyzed in the sotagliflozin 400 mg group.
- Randomized patients will be excluded from the safety population only if there is documented evidence (ie, all study dates recorded as no medication taken) that patients have not taken the study treatment. If a patient is dispensed double-blind IMP and is lost to follow-up without any documented evidence, the patient will be considered exposed.

### 2.3.3 Pharmacokinetic population

For PK analyses, the PK population is defined as all safety patients who contribute with at least 1 valid plasma concentration of sotagliflozin or its 3-O-glucuronide metabolite. The PK data will be analyzed according to the treatment actually received (See [Section 2.3.2](#)).

